Table 3	AE Reporting Timeframes and Process for Investigators and Vendors	41

LIST OF ABBREVIATIONS

AE	Adverse Event	
ALT	Alanine Transaminase	
ALT	Alanine Transaminase Aspartate Transaminase	
ARO	Academic Research Organization	
BD	Business Day	
BNP	Brain Natriuretic Peptide	
CD	· · · · · · · · · · · · · · · · · · ·	
	Calendar Day	
CEP	Cyclic Guanosine Monophosphate	
CFR	Code of Federal Regulations	
CHD	Congenital Heart Disease	
CRF	Case Report Form	
CRO	Contract Research Organization	
CTEPH	Chronic Thromboembolic Pulmonary Hypertension	
DMP	Data Management Plan	
EMA	European Medicine Agency	
EQ5D	EuroQoL questionnaire	
ERA	Endothelin receptor antagonist	
FDA	Food and Drug Administration	
FPE	First Patient Enrolled	
GCP	Good Clinical Practice	
GPP	Good Publication Practice	
GVP	Good Pharmacovigilance Practice	
ICH	International Conference of Harmonization	
IEC	Independent Ethics Committee	
INN	International Nonproprietary Name	
MedDRA	Medical Dictionary for Regulatory Activities	
MCV	Mean Corpuscular Volume	
MCH	Mean Corpuscular Hemoglobin	
MCHC	Mean Corpuscular Hemoglobin Concentration	
N/A	Not Applicable	
NMPA	National Medical Products Administration	
NO	Nitric Oxide	
NT-proBNP	N-terminal pro Brain Natiruretic Peptide	
WHO functional class	WHO Functional Class	
OM	Operating Manual	
OS	Observational Study	
РАН	Pulmonary Arterial Hypertension	
PAS	Post-Authorization Study	
PASS	Post-Authorization Safety Study	
PEA		
PH		
PSUR		
PV		
PH PSUR	Pulmonary Endarterectomy Pulmonary Hypertension Periodic Safety Update Report Pharmacovigilance	

MK-4836-001-01 FINAL PROTOCOL

SAE	Serious Adverse Event	
SAP	Statistical Analysis Plan	
STROBE	Strengthening the Reporting of Observational Studies	
	in Epidemiology	
VAS	Visual Analogue Scale	
VKA	Vitamin K Antagonists	
6MWT	6-Minute Walk Test	

MK-4836-001-01 FINAL PROTOCOL

2 ABSTRACT

Title	EXP osur E Registry R iocigua T in patients with pulmonary hypertension in China (EXPERT China)	
Protocol Number/ Version	MK-4836-001-01	
Date	27-Mar-2019	
Author	, MSD R&D (China) Co., Ltd.	
Rationale & Background	Pulmonary Arterial Hypertension (PAH) and Chronic Thromboembolic Pulmonary Hypertension (CTEPH) are rare and life-threatening diseases. Riociguat (Adempas [®]) is the first member of a new class of drugs, the sGC-stimulators (soluble guanylate cyclase-stimulators) and the first drug ever having shown efficacy in CTEPH. Riociguat has shown to be effective and well tolerated in patients with PAH and CTEPH randomized controlled trials. It is approved in China to treat patients with Persistent/recurrent after surgical treatment or inoperable CTEPH and patients with PAH. In accordance with the regulatory requirements this registry has been designed to collect information about the long-term safety of Adempas [®] in real clinical practice outside the regulated environment of a controlled clinical study.	
Research Question(s) & Objective(s)	The primary objective is the assessment of long-term safety of Adempas [®] in real life clinical practice.	
	In addition, it is going to prospectively collect data on clinical effectiveness, resource use, and how Adempas [®] is used by pulmonary hypertension (PH) experts under real-life conditions.	
Study Design	The EXPERT China registry is a national, multicenter, prospective, single-arm study collecting observational data from patients with PAH and CTEPH treated with Adempas [®] , within the approved indication and providing commercial drug at no cost.	
Population	Patients who have been prescribed Adempas [®] for a medically appropriate use will be eligible to be included into this registry. Indications and contraindications according to the local market authorization should be considered.	
Variables	Non-serious adverse event and serious adverse events will be captured, as well as all-cause mortality. Additional information will be provided for the documentation of symptomatic hypotension, hemoptysis and pulmonary hemorrhage as events of special interest. In addition, relevant information on medical	

	history, concomitant conditions and medications, resource use and clinical effectiveness will be captured.		
Data Sources	The investigator is requested to collect historic data (demographic and clinical characteristics) from medical records, and to collect treatment related data during visits that take place in routine clinical practice.		
Study Size	It is planned to enroll 80 patients including a reasonable proportion of patients newly starting Adempas [®] treatment. Enrollment of patients previously followed in the long-term extension of other riociguat studies is allowed.		
Data Analysis	All background variables and outcome parameters will analyzed descriptively with appropriate statistical metho categorical variables by frequency tables (absolute and relat frequencies) and continuous variables by summary statistics of mean, standard deviation, minimum, median, quartiles maximum). Continuous variables will also be described absolute value and as change from baseline per analysis to point, if applicable.		
	All analyses will be performed for the total study population (overall analysis) and separately for PH subtypes, patients who newly started or have already been on Adempas [®] and in patients receiving at least one dose of Adempas [®] . All statistical details will be described in the Statistical Analysis Plan (SAP).		
	It might have one interim analysis in the middle of the study on primary and secondary endpoints per the need decided by sponsor or authority.		
	A final analysis will be conducted at the end of the study.		
Milestones	Start of data collection (First Patient Enrolled, FPE) will be after Adempas [®] is commercially available in China. The recruitment period will be up to 14 months with an observation period of around 1 year. Data collection will continue until 30 days after the end of Adempas [®] therapy.		

3 AMENDMENTS AND UPDATES

PRIMARY REASON(S) FOR THIS AMENDMENT:

Section Number (s)	Section Title(s)	Description of Change (s)		Rationale
PASS INFORMATION	Author	(China) Co., Ltd.	, MSD R&D	To specify contact persons information
	MAH Contact Person	Healthcare Co. Ltd.	, Bayer	
PASS INFORMATION	Marketing authorization holder(s) (MAH)	"Bayer Pharma AG [name]" is updated to "Bayer AG [name]".		MAH update was approved in Sep 2018 in China by Bayer.
	LIST of ABBREVIATIONS	Add ALT, AST, BD, CD, FPE, NMPA,OS, PV, VKA Delete BMI, CCB, CFR, GVP, HEOR, ICD, OM, QPPV, WHO DD, WHO FC		Add missing abbreviations, spell out when used for the first time in text, delete abbreviations not applicable in this protocol.
1	RESPONSIBLE PARTIES	Update sponsor name: MSD R&D (China) Co., Ltd., Update the contact information from each party		To update the responsible parties and define sponsorship.
6.1.3	Strengths of study design	"an Adempas [®] clinical trial" is updated to "two Bayer Phase III clinical trials with riociguat".		To reflect the reality.
6.2.1	Eligibility	"local market authorization" is updated to "local Chinese label for Adempas [®] "		To emphasize that local Chinese label for Adempas [®] should be carefully considered by EXPERT China study investigator when assess patient eligibility.

Section Number (s)	Section Title(s)	Description of Change (s)	Rationale
6.2.2	Inclusion criterion/criteria	Inclusion criterion bullet 3: WHO Function Class II-III for patients newly treated with Adempas [®]	Patients have been treated with riociguat either currently in the CHEST and PATENT (riociguat) long term extension trials or started treatment with Adempas [®] after it was launched in China are different from drug naïve population. Patients under treatment might be on WHO Function Class I which is the result of improvement post- treatment and should be eligible for PASS study.
6.2.3	Exclusion criterion/criteria	Exclusion criterion bullet 1: Add the following: If a patient is currently in the CHEST or PATENT (riociguat) long term extension trials, then the patient can be considered for transition into EXPERT China study after the last dosing of riociguat.	To clarify the exclusion of participants from other interventional studies, except for CHEST or PATENT (riociguat) long term extension trials.
6.2.3	Exclusion criterion/criteria	 Add the following two bullet points to the list of exclusion criteria: Co-administration with specific PDE-5 inhibitors (such as sildenafil, tadalafil or vardenafil) or nonspecific PDE inhibitors (such as dipyridamole or theophylline) (see Section 6.3.16). Co-administration with nitrates or nitric oxide donors (such as amyl nitrite) in any form (see Section 6.3.16). 	To indicate specific PDE-5 inhibitors, non- specific PDE inhibitors and nitric oxide donors are also prohibited medication.

Section Number (s)	Section Title(s)	Description of Change (s)	Rationale
6.3.16	Prior and concomitant medication	Add a bullet point: Nitrates or nitric oxide donors (physician will be alerted that the combination of PDE5 inhibitors with Adempas [®] is contraindicated)	Nitric oxide donors are also prohibited medication.
6.7.1	Statistical considerations	It might have one interim analysis in the middle of the study on primary and secondary endpoints per the need decided by sponsor or authority.	To clarify that one interim analysis may be conducted to evaluate safety/ meet agency requirement, which is consistent with Section 2 Abstract.
6.8	Quality Control	"MSD China" is removed	"Sponsor and MSD China" is standard language but not applicable in this studySponsor and MSD China refer to the same legal entity: MSD R&D (China) Co., Ltd.
7.6	Dose Titration	If at any time, the patient has systolic blood pressure lower than 95 mmHg with symptoms and/or signs of hypotension, decrease the dosage by 0.5 mg taken three times a day.	To give a clear definition of "low systolic blood" pressure AND symptoms and/or signs of hypotension. This is consistent with the drug label.
7.7	Dose Interruption	The definition of "Adempas [®] is interrupted for 3 days or more" is 9 consecutive doses or more.	To clarify the definition and keep consistent understanding and operation at site.
9.2.4	Non-serious Adverse Reaction (NSAR)	An adverse reaction that does not meet any of the serious criteria in Section 9.2.3.	To correct the typographical error indicating the serious criteria source is in Section 10.2.3.

Section Number (s)	Section Title(s)	Description of Change (s)	Rationale
9.2.6	Health Outcome of Interest (HOI)	Not applicable	Health Outcome of Interest that is a standard section but not applicable in this study. This section and corresponding content in Sections 9.1.1 and 9.1.3 is removed.

056JT5

4 RATIONALE AND BACKGROUND

Pulmonary Arterial Hypertension (PAH) is a rare, progressive and life-threatening disease. It is characterized by a chronic increase in pulmonary vascular resistance (PVR), due to progressive vascular remodeling that can ultimately lead to right heart failure and death [1,2]. Symptoms of PAH are related to right heart failure and include exercise-induced dyspnea, exhaustion, leg edema and decreased quality of life. In untreated patients with idiopathic PAH, the life expectancy is reduced to 2.8 years after diagnosis, whereas in contemporary registries in the era of modern PAH-specific treatments the survival rates have increased to 83% and 58% at 1 and 3 years respectively [3,4]. The incidence is currently estimated as 2.4 cases per million adult inhabitants per year with a prevalence of 15 cases per million adult inhabitants [5]. Available PAH-specific treatments include prostacyclin analogues, endothelin receptor antagonists, and PDE5-inhibitors. The available drugs predominantly act as vasodilators and improve exercise capacity [6]. Despite advances in the clinical management based on these available therapies for PAH, there is still significant unmet medical need for improvement as the mortality of patients with PAH remains high (15% at 1 year and 32% at 3 years) [7].

Chronic Thromboembolic Pulmonary Hypertension (CTEPH) is a different progressive and life-threatening type of pulmonary hypertension. Whereas symptoms, as well as epidemiology, of CTEPH are similar compared with PAH, there are significant differences regarding etiology, diagnosis and treatment [8,9]. In CTEPH the increase in pulmonary vascular resistance is a result of a pulmonary artery obstruction by residual organized thrombi [10]. A ventilation-perfusion scan is important for differential diagnosis as a normal scan excludes CTEPH [11]. The standard and potentially curative treatment for CTEPH is pulmonary endarterectomy (PEA). However, 20 to 40% of patients are not eligible for surgery and in 10-15% of patients PH may persist or reoccur after surgery [12-15]. Specific PAH drugs had failed in the past to show efficacy in inoperable CTEPH and before Adempas[®] no drug treatment has been approved for these patients [16].

Adempas[®] is the first member of a new class of drugs, the sGC-stimulators (soluble guanylate cyclase-stimulators). It restores the NO-sGC-cGMP pathway and leads to increased generation of cyclic guanosine monophosphate (cGMP) which plays an important role in regulating vascular tone, proliferation, fibrosis, and inflammation. Adempas[®] directly stimulates sGC independently of nitric oxide (NO), while also increasing the sensitivity of sGC to NO. This appears to be of importance as pulmonary hypertension is associated with pulmonary endothelial dysfunction and can be related to low levels of NO [17-21].

Adempas[®] is the first drug that could demonstrate robust efficacy in two placebo-controlled, multicenter trials in two different indications of pulmonary hypertension. In the CHEST-1 study, Adempas[®] showed for the first time robust clinical efficacy in patients with inoperable chronic thromboembolic pulmonary hypertension and in patients with persistent CTEPH after surgery by significantly improving exercise capacity as well as relevant secondary endpoints such as hemodynamics and WHO functional class. In the PATENT-1 study in pulmonary arterial hypertension patients, Adempas[®] showed significant improvement in exercise capacity in treatment-naïve patients as well as in patients pre-

treated with endothelin receptor antagonists (ERAs) or non-intravenous prostacyclin analogues. At the same time, a consistent significant improvement across the secondary endpoints including hemodynamics, WHO functional class and time to clinical worsening could be demonstrated. In both studies, Adempas[®] was well tolerated with a good safety profile [22,23].

Adempas was approved in China in Sep 2017. It's approved to treat the patients with the following indications:

Chronic thromboembolic pulmonary hypertension (CTEPH)

For the treatment of adult patients with WHO Functional Class (FC) II to III with persistent/recurrent CTEPH after surgical treatment, or inoperable CTEPH, to improve exercise capacity.

Pulmonary arterial hypertension (PAH)

As monotherapy, or in combination with endothelin receptor antagonists or prostanoid, is indicated for the treatment of adult patients with pulmonary arterial hypertension (PAH) with WHO Functional Class (FC) II to III to improve exercise capacity. The confirmatory trial enrolled the

PAH population including aetiologies of idiopathic or heritable PAH or PAH associated with connective tissue disease with WHO-FC II to III.

According to the request from China health authority, the Adempas[®] registry study is planned. The registry is a multicenter prospective study of patients treated with Adempas[®] in accordance with the local label. It will capture data from patients with Adempas[®] treatment in a real-life clinical setting and outside the regulated environment of a controlled clinical study.

The objective of the registry is to describe the safety profile of Adempas[®] under clinical practice conditions. In addition, the registry offers a structured prospective collection of data on the clinical effect, patient-reported outcomes and resource use and to gather information on how Adempas[®] is used by PH experts.

In agreement with EMA, EXPERT, a global, multicenter, prospective, uncontrolled, noninterventional cohort registry of patients treated with commercial riociguat, designed to collect information about the long-term safety of Adempas[®] in real clinical practice outside the regulated environment of a controlled clinical study, was implemented. The proposed China registry is based on the EXPERT study considering local regulatory requirements. Also considering the difficulty of local patients' affordability sponsor will provide Adempas with no charge. However, it won't change the nature of observational data in the medical practice.

5 RESEACH QUESTION AND OBJECTIVES

5.1 Primary Objective

The primary objective is the assessment of long-term safety of Adempas[®] in real life clinical practice.

5.2 Secondary Objective(s)

The secondary objectives in this study are:

- Long-term safety of Adempas[®] in the different PH indications (PAH, CTEPH)
- Effectiveness of Adempas[®] in the long-term follow-up of PH patients
- Information on resource use
- Information on how Adempas[®] is used (e.g. indication and indication subgroups, dose)

6 RESEARCH METHODS

6.1 Study Design

This registry is a national, multicenter, prospective, single-arm study of patients who will be treated with commercial riociguat for the locally approved indications of PH. The study will start after Adempas[®] has been authorized and made commercially available in China.

All patients prescribed with Adempas[®] for a medically appropriate use, consent to participate, and fulfill the selection criteria are eligible for enrollment into the study. Once enrolled, all aspects of the study will be conducted in an observational manner with no additional visits, procedures, etc. required as part of the study. All decisions on clinical management of the patient, including the actual treatment duration will be determined solely by the physician.

Patients will be followed up for an observation period of at least 1 year or until 30 days after end of Adempas[®] therapy. The enrollment period to obtain the required 80 patients is expected to be up to 14 months. Patient's clinical information will be documented at time of the initial visit and approximately every three to six months according to routine clinical practice thereafter. Data collection will continue until 30 days after the end of Adempas[®] therapy. Serious adverse events will be followed up until resolution.

Considering the difficulty of affordability of local patients during the study, sponsor will provide drug with no charge once medical decision on the prescription is made by physician and patients signed the informed consent. The free drug will be provided from the date of the first patient in to one year after the last patient in.

6.1.1 **Primary Endpoint(s)**

The primary endpoints are:

- Incidence of adverse events/serious adverse events
- Incidence of all-cause mortality

6.1.2 Secondary Endpoint(s)

The secondary endpoints are:

Safety

- Incidence of AE (Adverse Event) and SAE (Serious Adverse Event) in the different PH indications (PAH, CTEPH)
- Incidence of AE of interest overall and in the different PH indications (PAH, CTEPH)

Effectiveness

- Clinical effect in the follow-up of PH patients as compared with baseline, if both baseline and post baseline measurements are available
 - 6-minute walk test
 - WHO FC
 - Borg dyspnoea index
 - Biomarkers (BNP, NT-pro BNP)
 - EQ5D VAS
 - Haemodynamic parameters from right heart catheter measurement

Resource use

- Hospitalization/ outpatient visits
- Administration and any change in drug treatment for PAH or CTEPH

6.1.3 Strengths of Study Design

In this therapeutic area a multicenter exposure registry with a mix of patients previously enrolled in two Bayer Phase III clinical trials with riociguat and patients newly starting Adempas[®] allows for a structured prospective documentation of long-term data on safety, clinical effect, and information on how Adempas[®] is used by PH experts. As Adempas[®] is the first sGC-stimulator in clinical use and all available clinical data in Chinese patients derive from well-defined clinical studies, this registry may collect additional data on important potential safety risks, drug interactions and missing information.

6.2 Setting

6.2.1 Eligibility

Patients who have been prescribed Adempas[®] for a medically appropriate use will be eligible to be included into this registry. Indications and contraindications according to the local Chinese label for Adempas[®] should be carefully considered.

6.2.2 Inclusion Criterion/Criteria

- Patients who have been diagnosed with PAH or CTEPH
- Female and male patients who start or are on treatment with Adempas®
- WHO Function Class II-III for patients newly treated with Adempas®
- Written informed consent

6.2.3 Exclusion Criterion/Criteria

• Patients currently participating in an interventional clinical trial (If a patient is currently in the CHEST or PATENT (riociguat) long term extension trials, then the patient can be considered for transition into EXPERT China study after the last dosing of riociguat.)

- Female patient who is pregnant
- Patients with severe hepatic impairment (Child Pugh grade C)
- Patients with SBP<95 mmHg when newly treated with Adempas[®]
- Patients who have been diagnosed with idiopathic interstitial pneumonia
- Co-administration with specific PDE 5 inhibitors (such as sildenafil, tadalafil or vardenafil) or nonspecific PDE 5 inhibitors (such as dipyridamole or theophylline) (see Section 6.3.16).
- Co-administration with nitrates or nitric oxide donors (such as amyl nitrite) in any form (see Section 6.3.16).
- Any condition which, in the opinion of the investigator may confound the results or result in unwarranted risk in administering Adempas[®] to the patient.

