6.2.7 Representativeness

Source population of the present study is patients with PH, specifically PAH and CTEPH. Patients with this rare condition are mostly diagnosed and managed in specialized centers. This includes the initiation and any change of specific drug therapy. The participation of these specialized centers into the registry, the consecutive recruiting of patients and the broad definition of selection criteria is going to ensure the representativeness of the study population.

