6.7.6 Bias, Confounding and Effect-Modifying Factors

While study drug will be provided, the data collection is being based on real life clinical practice, including timing of visits, treatment, and evaluation. There are several potential sources of bias including missing data, misclassification, recall bias, reporting bias, survivor bias, as well as selection biases. To reduce patient selection bias physicians must document that they have tried to recruit consecutive eligible patients who receive Adempas[®].

To decrease the reporting bias, 100% source data verification will be performed on critical study data. Detailed information will be described in site monitoring plan (SMP). For survivor bias, see Section 6.9.

Baseline characteristics of the patients will be examined and described in detail.

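### An open-ended exclusion for conditions that might confound the results sits badly with a real-life safety registry, lies outside the consecutive-recruitment safeguard, and could bias event incidence low

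*Protocol*

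**What the plan says.** Protocol 6.2.3 ends its exclusion list with a discretionary bullet: any condition that "in the opinion of the investigator may confound the results or result in unwarranted risk in administering" Adempas. It has two limbs joined by an or, so a condition that adds no risk can still exclude a patient if the investigator thinks it might confound.

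Four other places bear on this bullet:

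- **Objective (5.1).** "The primary objective is the assessment of long-term safety of Adempas" in everyday practice.
- **Representativeness (6.2.7).** Besides the participation of specialised centres, the protocol relies on two features: "the consecutive recruiting of patients and the broad definition of selection criteria is going to ensure the representativeness of the study population".
- **Safeguard (6.7.6).** "To reduce patient selection bias physicians must document that they have tried to recruit consecutive eligible patients" who receive the drug.
- **Stated strength (6.1.3).** The protocol says that "this registry may collect additional data on important potential safety risks, drug interactions and missing information".

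The study is single-arm (6.1) and its analyses are descriptive (6.7.1). Section 8.2 keeps the decision to prescribe separate from the decision to include a patient, so a patient can be prescribed the drug and not be enrolled.

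**The concern.** An exclusion for possible confounding is usual where a treatment effect is to be isolated. Here the primary output is a count of adverse events, serious adverse events and deaths in users of one drug, whatever their cause. For that purpose, patients with other diseases or several medicines belong to the target population.

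The protocol itself wants to see such patients. Section 6.3.4 collects cancer, diabetes, vascular disease, haemoptysis history, and hepatic and renal impairment. Section 6.7.3 plans strata by hepatic impairment, renal impairment and concomitant medication. A site could, for example, read a history of haemoptysis as confounding haemoptysis, which is an event of interest (6.3.2).

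At stake are the level of the primary incidences and the representativeness claim. The protocol states no count of patients prescribed but not enrolled, so a reader of the report could not tell how much selection had taken place.

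**Working it through.** **1. The protocol's own figures.** It gives no figure for how often the bullet will be used or for the event risk of those excluded. Its only size calculation is for accrual in 6.5: 109 patients in over 2 years, scaled to 1.5 years. This gives 109 × 1.5 / 2 = 81.75, against 81 stated. It reproduces and has no bearing on this point.

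**2. Does the safeguard reach these patients?**

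- 6.7.6 asks for documented attempts to recruit consecutive patients who are eligible.
- A patient ruled out under 6.2.3 is by definition not eligible.
- A site could therefore apply the confounding limb freely and still comply fully with 6.7.6.

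**3. Is the selection acknowledged elsewhere?** Section 6.7.6 names selection bias in general. Section 6.9 discusses survivor bias and small sample size. Neither mentions this bullet.

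**4. Direction and size.** Let f be the share of treated patients excluded under the limb, p0 the incidence in those kept, and RR the incidence ratio of excluded to kept patients.

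- Incidence in all treated patients = (1 − f) × p0 + f × p0 × RR
- Incidence the registry reports = p0
- Reported minus true = −f × p0 × (RR − 1)

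The bias is downward if RR exceeds 1, and zero if RR is 1 or f is 0. The inputs below are all assumptions, none from the documents: p0 = 20%, f = 5% to 20%, RR = 1 to 2.

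| f | RR | Incidence in all treated | Reported | Shortfall (points) |
|---|---|---|---|---|
| any | 1 | 20% | 20% | 0 |
| 5% | 1.5 | 20.5% | 20% | 0.5 |
| 5% | 2 | 21% | 20% | 1 |
| 10% | 1.5 | 21% | 20% | 1 |
| 10% | 2 | 22% | 20% | 2 |
| 20% | 1.5 | 22% | 20% | 2 |
| 20% | 2 | 24% | 20% | 4 |

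For example, 0.8 × 20% + 0.2 × 40% = 24%. The largest relative shortfall in the table is 4/24 = 17%.

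**5. Scale against sampling error.** With 80 patients and 16 events (20%), the exact 95% interval is 11.9% to 30.4%. A bias of this size would not show in the data. Unlike sampling error, it would not shrink with more patients.

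**The case against.** The strongest reply is that the bullet names no disease and the rest of the protocol points towards inclusion. Sites are told to record the comorbidities in question, strata are planned for them, and investigators are trained on the objectives (6.8). Free drug goes only to consenting, enrolled patients, because affordability is a problem (6.1, 7.2.2). About 10 active centres must find 80 patients with a rare disease (6.5). All of this discourages heavy use of the limb. It stands as a reason to expect f to be small, but it does not limit what the text allows.

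Four stronger readings are tempting and are not supported:

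- **That incidence will be biased low.** This needs both material use of the limb and a higher event rate in those excluded, and the documents quantify neither. Section 6.9 says baseline characteristics and associated conditions strongly influence survival in PAH. That supports the direction for mortality, not for adverse events in general.
- **That the bullet contradicts 6.1.** The sentence there opens with "All patients prescribed with Adempas" but goes on to make enrolment subject to the selection criteria. It is not evidence of a conflict.
- **That the limb has no purpose at all.** There are change-from-baseline effectiveness endpoints (6.1.2, 6.7.4) and a causality judgement for each event (9.2.2, 9.2.7), and a coexisting condition can blur both. However, 9.2.2 already tells the investigator to weigh concomitant disease and medication event by event, so excluding the patient beforehand is not the only remedy.
- **That the limb empties the risk strata.** No such loss can be derived. Separate bullets already remove Child-Pugh C, PDE-inhibitor and nitrate users, and their effect cannot be told apart from this one.

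One further point stands: the risk limb, which would remain, could exclude some of the same patients. Deleting the confounding limb cannot be credited with recovering the whole shortfall.

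**Conclusion.** The point holds as a defect of wording with a possible, unquantified effect. The confounding limb is unlimited, serves the primary objective poorly, weakens the assurance of representativeness in 6.2.7, and falls outside the only selection safeguard. That much follows from the text alone.

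The effect on incidence is conditional. Under the illustrative inputs the shortfall is 0 to 4 percentage points, and it is zero if the limb is never used or the excluded patients have the same risk. Confidence is high in the textual tension and low in any particular size. It is worth changing because the change is cheap and protects the primary objective, not because a bias has been shown.

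**What to change.** 1. In Protocol 6.2.3, remove the confounding limb from the last bullet. Keep the auxiliary verb that governs both limbs, so that the risk limb reads as it does now. Leave the risk limb and all label-based criteria unchanged; no clinical rule is touched.
2. In 6.7.6, have the consecutive-recruitment record count every patient prescribed Adempas at the site, not only the eligible ones. Give an anonymous reason for each non-enrolment: no consent, label contraindication, or investigator judgement of risk.
3. Report that count, by reason, in the study report, so that any selection remaining through the risk limb can be measured.

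Cost: one phrase in an amendment and a short log per site, with no added visits. More complex patients may make the effectiveness changes and causality judgements somewhat noisier. That is an acceptable price where safety is the primary objective.
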